3.3. Strata and Covariates

Subjects will be randomly assigned to treatment groups via the interactive voice or web response system (IXRS) in a 1:1 ratio using a stratified randomization schedule. Stratification will be based on screening for HBeAg status (HBeAg-negative vs HBeAg-positive) and age (\geq 50 or < 50 years). For statistical analyses, the HBeAg status and age strata recorded in the clinical database will be reclassified using the corresponding baseline value and used for analysis. If the number of subjects in a stratum is too small, the stratum may be combined with other strata for analysis.

3.4. Missing Data and Outliers

3.4.1. Missing Data

A missing datum for a given study analysis window may be due to any of the following reasons:

- A visit occurring in the window but data were not collected or were unusable
- A visit not occurring in the window
- A subject permanently discontinuing from the study before reaching the window

In general, values for missing data will not be imputed, unless methods for handling missing data are specified.

For missing last dosing date of study drug, imputation rules are described in Section 3.6. The handling of missing or incomplete dates for AE onset is described in Section 7.1.6.2, and for concomitant medications in Section 7.7.

3.4.2. Outliers

Outliers will be identified during the data management and data analysis process, but no sensitivity analyses will be conducted. All data will be included in the data analysis.

3.5. Data Handling Conventions and Transformations

In general, age (in years) on the date of the first dose of study drug will be used for analyses and presentation in listings. If an enrolled subject was not dosed with any study drug, the randomization date will be used instead of the first dosing date of study drug. For screen failures, the date the informed consent was signed will be used for age calculation. If only the birth year is collected on the eCRF, "01 July" will be used for the unknown birth day and month for the purpose of age calculation. If only birth year and month are collected, "01" will be used for the unknown birth day.

Non-PK data that are continuous in nature but are less than the lower limit of quantitation (LOQ) or above the upper LOQ will be imputed as follows:

- A value that is 1 unit less than the LOQ will be used to calculate descriptive statistics if the datum is reported in the form of "< x" (where x is considered the LOQ). For example, if the values are reported as < 50 and < 5.0, values of 49 and 4.9, respectively, will be used to calculate summary statistics. An exception to this rule is any value reported as < 1 or < 0.1, etc. For values reported as < 1 or < 0.1, a value of 0.9 or 0.09, respectively, will be used to calculate summary statistics.
- A value that is 1 unit above the LOQ will be used to calculate descriptive statistics if the datum is reported in the form of "> x" (where x is considered the LOQ). Values with decimal points will follow the same logic as above.
- The LOQ will be used to calculate descriptive statistics if the datum is reported in the form of " \leq x" or " \geq x" (where x is considered the LOQ).

Logarithm (base 10) transformations will be applied to HBV DNA and quantitative HBsAg data, as appropriate, in efficacy analyses.

For HBV DNA, if the value in IU/mL is above the upper limit of quantification, the corresponding diluted value, if available, will be used. HBV DNA results of "<20 IU/mL HBV DNA detected" or "No HBV DNA detected" will be imputed as 19 IU/mL.

3.6. Analysis Visit Windows

3.6.1. Definition of Study Day 1 and Other Definitions

Study Day 1 is defined as the day when the first dose of blinded study drug was taken, as recorded on the Study Drug Administration eCRF.

Open-Label Study Day 1 is defined as the day when the first dose of the open-label study drug was taken, as recorded on the Study Drug Administration eCRF.

Study days are calculated relative to Study Day 1. For events that occurred on or after Study Day 1 date, study days are calculated as (visit date Study Day 1 + 1). For events that occurred prior to Study Day 1, study days are calculated as (visit date Study Day 1).

Open-Label Study days are calculated relative to Open-Label Study Day 1. For events that occurred on or after Open-Label Study Day 1, study days are calculated as (visit date Open-Label Study Day 1+1).

Follow-up days are for visits occurred during the treatment-free follow-up period and calculated as (visit date last dose date).

Last Dose Date of Blinded Study Drug is the latest non-missing end date of blinded study drug, recorded on the Study Drug Administration eCRF form with "Study Drug Permanently Withdrawn" box checked for subjects who prematurely discontinued blinded study drug or who completed blinded study drug according to the Blinded Study Drug Completion eCRF. If the last dose date of blinded study drug is missing (eg, due to lost to follow up) for subjects who prematurely discontinued blinded study drug or completed blinded study drug, or for subjects who are still on blinded study drug, the latest of non-missing blinded study drug start dates and end dates, the clinical visit dates, and the laboratory visit dates, excluding the dates during openlabel treatment and 24-week treatment-free follow up, will be used to impute the last dose date of blinded study drug.

For subjects who prematurely discontinued blinded study drug or who completed blinded study drug but did not enter the open-label phase, the **Last Dose Date** is the same as Last Dose Date of Blinded Study Drug.

For subjects who completed blinded study drug and entered the open-label phase, the Last Dose Date is the latest non-missing end date of open-label study drug, recorded on the Study Drug Administration eCRF form with "Study Drug Permanently Withdrawn" box checked for subjects who prematurely discontinued open-label study drug or who completed open-label study drug according to Open-Label Study Drug Completion eCRF. If the last dose date of open-label study drug is missing (eg, due to lost to follow up) for subjects who prematurely discontinued open-label study drug or who completed open-label study drug, or for subjects who are still on open-label study drug, the latest of non-missing open-label study drug start dates and end dates, the clinical visit dates, and the laboratory visit dates, excluding the dates during 24-week treatment-free follow-up, will be used to impute the last dose date.

Last Study Date is the latest of nonmissing study drug (blinded or open-label) start dates and end dates, the clinical visit dates, and the laboratory visit dates, including the 24-week treatment-free follow-up visit date, for subjects who prematurely discontinued study or who completed study according to the Study Completion eCRF.

3.6.2. Analysis Windows

Subject visits might not occur on protocol specified days. Therefore, for the purpose of analysis, observations will be assigned to analysis windows.

The following windows (Table 3-1 to Table 3-6) apply only to baseline and postbaseline on-treatment assessments collected during the double-blind phase and open-label phase. For summaries and analyses, assessments will first be categorized into baseline and postbaseline on-treatment assessments occurring during the double-blind or open-label phase before applying analysis windows.

Baseline value for the double-blind phase is defined as the last nonmissing value obtained on or prior to Study Day 1. For DXA BMD, it is defined as the last value on or prior to Study Day 14.

For subjects who completed blinded study drug and entered the open-label phase, laboratory assessments that occurred during the period from Study Day 2 up to and including the minimum of the Last Dose Date of Blinded Study Drug + 3 days and Open-label Study Day 1, will be considered as postbaseline on-treatment assessments during the double-blind phase. If a subject prematurely discontinued blinded study drug or did not enter open-label phase after completion of blinded study drug, then postbaseline on-treatment assessments during the double-blind phase will be defined as assessments that occurred during the period from Study Day 2 up to and including the Last Dose Date of Blinded Study Drug + 3 days. DXA assessments that occurred during the period from Study Day 15 up to and including the Last Dose Date of Blinded Study Drug + 14 days will be considered as postbaseline on-treatment assessments during the double-blind phase.

Baseline value for the open-label phase is defined as the last nonmissing value obtained on or prior to Open-Label Study Day 1. For DXA BMD, it is defined as the last value on or prior to Open-Label Study Day 14.

For subjects who entered the open-label phase, postbaseline on-treatment assessments during the open-label phase will be defined as assessments that occurred during the period from Open-label Study Day 2 up to the Last Dose Date + 3 days. DXA assessments that occurred during the period from Open-label Study Day 15 up to the Last Dose Date + 14 days will be considered as postbaseline on-treatment assessments during the open-label phase.

Baseline value for the TFFU phase is defined as the last nonmissing value obtained on or prior to the Last Dose Date + 3 days.

The analysis windows for HBV DNA, hematology, serum chemistry and liver function tests, urinalysis, urine pregnancy test, eGFR_{CG}, bone biomarker serum parathyroid hormone (PTH), urine fractional excretion of filtered phosphate (FEPO₄), renal tubular maximum reabsorption rate of phosphate to the glomerular filtration rate (TmP/GFR), urine protein to creatinine ratio

(UPCR), urine albumin to creatinine ratio (UACR), weight, and vital sign assessments are presented in Table 3-1.

Table 3-1.

Analysis Windows for HBV DNA, Hematology, Serum Chemistry and Liver Function Tests, Urinalysis, Urine Pregnancy Test, eGFR_{CG}, PTH, FEPO₄, TmP/GFR, UPCR, UACR, Weight, and Vital Sign Assessments

Visit ID	Nominal Day	Lower Limit	Upper Limit
Baseline			1
Week 4	28	2	42
Week 8	56	43	70
Week 12	84	71	126
Week 24	168	127	210
Week 36	252	211	294
Week 48	336	295	378
Week 60	420	379	462
Week 72	504	463	588
Week 96	672	589	840

The analysis windows for safety ECG and Child Pugh Score are presented in Table 3-2.

Table 3-2. Analysis Windows for Safety ECG and Child Pugh Score

Visit ID	Nominal Day	Lower Limit	Upper Limit
Baseline			1
Week 48	336	2	504
Week 96	672	505	840

The analysis windows for FibroTest and health-related quality of life questionnaires are presented in Table 3-3.

Table 3-3. Analysis Windows for Fibrotest and Health Related Quality of Life Questionnaires

Visit ID	Nominal Day	Lower Limit	Upper Limit
Baseline			1
Week 24	168	2	252
Week 48	336	253	504
Week 96	672	505	840

The analysis windows for BMD results from DXA are presented in Table 3-4.

Table 3-4. Analysis Windows for BMD Results from DXA

Visit ID	Nominal Day	Lower Limit	Upper Limit
Baseline			14
Week 24	168	15	252
Week 48	336	253	420
Week 72	504	421	588
Week 96	672	589	840

The analysis windows for fasting glucose, fasting lipid panel including total cholesterol, high density lipoprotein (HDL), direct low density lipoprotein (LDL), total cholesterol to HDL ratio, and triglycerides, serum HBsAg (quantitative) and HBV serology are presented in Table 3-5.

Table 3-5. Analysis Windows for Fasting Glucose, Fasting Lipid Panel, Serum HBsAg (Quantitative) and HBV Serology

Visit ID	Nominal Day	Lower Limit	Upper Limit
Baseline			1
Week 12	84	2	126
Week 24	168	127	210
Week 36	252	211	294
Week 48	336	295	378
Week 60	420	379	462
Week 72	504	463	588
Week 96	672	589	840

The analysis windows for fasting renal biomarkers including urine retinol binding protein (RBP), urine RBP to creatinine ratio, urine beta-2-microglobulin (B2M), urine B2M to creatinine ratio, and bone biomarkers including C-type collagen sequence (CTX), procollagen type 1 N-terminal propeptide (P1NP) are presented in Table 3-6.

Table 3-6. Analysis Windows for Fasting Renal and Bone Biomarkers

Visit ID	Nominal Day	Lower Limit	Upper Limit
Baseline			1
Week 4	28	2	56
Week 12	84	57	126
Week 24	168	127	252
Week 48	336	253	420

Visit ID	Nominal Day	Lower Limit	Upper Limit
Week 72	504	421	588
Week 96	672	589	840

Post-treatment assessments during the treatment free follow-up (TFFU) phase will be defined as assessments that occurred during the period after the Last Dose Date (LDD) + 3 days up to the Last Study Date.

The analysis windows for post-treatment assessments are presented in Table 3-7.

Table 3-7. Analysis Windows for Post-Treatment Assessments

Visit ID	Nominal Follow-Up Day	Lower Limit	Upper Limit
Follow-Up Week 4	28	LDD+4	42
Follow-Up Week 8	56	43	70
Follow-Up Week 12	84	71	98
Follow-Up Week 16	112	99	126
Follow-Up Week 20	140	127	154
Follow-Up Week 24	168	155	182

3.6.3. Selection of Data in the Event of Multiple Records in an Analysis Visit Window

Depending on the statistical analysis method, single values are required for each analysis window. For example, change from baseline by visit usually requires a single value, whereas a time-to-event analysis would not require one value per analysis window. When a single value is needed, the following rule(s) will be used.

For baseline of the double-blind, open-label, and TFFU phases, the last available record on or prior to the first dose of blinded study drug, open-label study drug, and last dose date + 4 days will be selected, respectively. For DXA BMD baseline, the last value on or prior to Study Day 14 and Open-Label Study Day 14 will be selected for the double-bind and open-label phases, respectively. If there are multiple records with the same time or no time recorded on the same day for numeric observations, the average will be computed for that day, except for HBV DNA and quantitative HBsAg the geometric mean will be taken instead. If there are multiple records with the same time or no time recorded on the same day for categorical observations, the most conservative value will be taken, eg, negative will be selected over positive for HBeAg and HBsAg, and positive will be selected over negative for HBeAb and HBsAb.

The following specified rules will be used for postbaseline visits:

- **ALT:** The largest value will be included in the analysis when 2 or more ALT values occur within the same visit window.
- **BMD:** The latest record in the window will be selected
- **HBV DNA (IU/mL):** The record on the latest day in the window will be selected. If there is more than 1 record on the selected day, the geometric mean will be taken.
- Quantitative HBsAg (IU/mL): The record closest to the nominal day for that visit will be selected. If there are 2 records equidistant from the nominal day, the latest will be selected. If there is more than 1 record on the selected day, the geometric mean will be taken.
- **Serology:** For HBeAg, HBeAb, HBsAg, and HBsAb, the record closest to the nominal day for that visit will be selected. If there are 2 records equidistant from the nominal day, the latest will be selected. If there is more than 1 record on the selected day, the most conservative value will be taken, ie, positive will be selected over negative for HBeAg and HBsAg, and negative will be selected over positive for HBeAb and HBsAb.

For all other laboratory parameters:

• If multiple valid non-missing **numeric** observations exist in a window, then records will be chosen as follows:

The record closest to the nominal day for that visit will be selected. If there are 2 records equidistant from the nominal day, the latest will be selected. If there is more than 1 record on the selected day, the average will be taken.

• If multiple valid non-missing **categorical** observations (eg, safety ECG results) exist in a window, then records will be chosen as follows:

The most conservative value (eg, abnormal will be selected over normal for safety ECG) within the window will be selected. In the event that 2 values within a window are of equal abnormality, the value collected nearest to the nominal date will be used.

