Subjects with HBsAg loss, and confirmed seroconversion to anti-HBs should discontinue study drug within 3-6 months following confirmation of seroconversion to anti-HBs. Subjects with HBsAg loss with confirmed seroconversion prior to Week 48 are not permitted to discontinue study drug prior to the Week 48 visit. Subjects with HBsAg loss with confirmed seroconversion will be followed off treatment every 4 weeks for 12 weeks and then per the study visit schedule (Appendix 2) through Week 96/ED. Discontinuation of study drug for subjects experiencing HBsAg loss with confirmed seroconversion, who have known bridging fibrosis or cirrhosis, should be considered on a case by case basis.

The primary analysis will occur at Week 48 with the primary efficacy endpoint being the proportion of subjects with HBV DNA \geq 20 IU/mL, as determined by the modified US FDA-defined snapshot algorithm.

An external, independent, multidisciplinary DMC will review the progress and safety of this study. The committee will convene after the last subject enrolled completes Week 24 of the study. However, Gilead will defer to the DMC for any decision to convene earlier or more frequently. At each meeting, the DMC will review routine safety and DXA data and will make recommendations regarding modification of the study treatment.

Subjects with a history of or current diagnosis of compensated cirrhosis (i.e. those with cirrhosis without laboratory or clinical evidence of decompensated liver disease) are eligible for enrollment. Acceptable diagnostic criteria for cirrhosis include a Metavir or Knodell fibrosis score ≥ 4 or Ishak fibrosis score ≥ 5 by liver biopsy, a Fibrotest score ≥ 0.75 , or previous Fibroscan result > 12kPa (in countries where locally approved). Available information regarding the presence or absence of cirrhosis by these criteria will be captured in the electronic case report forms at Baseline, and any other time during the trial should an investigator opt to undertake additional studies. Available information regarding hepatic status will be assessed by Child-Pugh score and will be captured in the electronic case report forms at Baseline, Weeks 48 and 96. The change in fibrosis as assessed by Fibrotest[®] will be performed in all subjects participating in the trial at Baseline, and Weeks 48, and 96/ED.

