6.4. Post-Treatment Assessments

6.4.1. HBsAg Loss and Seroconversion Subjects

Subjects who discontinue study drug due to HBsAg loss with confirmed seroconversion to anti-HBs on or after the Week 48 visit, will be followed off treatment every 4 weeks for 12 weeks and then per the original study visit schedule through Week 96/ED (excluding drug dispensation and accountability).

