6.5. Assessments for Premature Discontinuation from Study

If a subject discontinues study dosing (for example, as a result of an AE), every attempt should be made to keep the subject in the study and continue to perform the required study-related follow-up and procedures (see Section 6.6, Criteria for Discontinuation of Study Treatment). If this is not possible or acceptable to the subject or investigator, the subject may be withdrawn from the study.

The ED Visit should be performed within 72 hours (i.e., visit window is \pm 3 days) of the last study drug dose.

- Complete physical exam with vital signs (blood pressure, pulse, respiration rate and temperature) and body weight
- ECG (subjects must rest quietly in the supine position for a minimum of 5 minutes prior to the recording)
- DXA scan of spine and hip to be performed within ±14 days of the expected visit date and is done only if not done within the past 12 weeks of the ED visit
- Review concomitant medications
- Review adverse events
- Fasting blood sample for bone biomarkers and metabolic assessment (glucose and lipid panel [total cholesterol, HDL, direct LDL, and triglycerides]) no food or drinks, except water, at least 8 hours prior to blood collection (only collected if not done in the last 12 weeks)
- Fasting urine sample for renal biomarkers (only collected if not done in the last 12 weeks)
- Blood sample for serum chemistry and liver function tests, hematology, PT/INR, plasma HBV DNA, serum HBsAg (quantitative), HBV serology (qualitative HBsAg and HBeAg), virology (resistance surveillance), PPD
- Estimated creatinine clearance (using the Cockcroft-Gault method)
- Blood sample for Fibrotest[®]
- Child-Pugh Score (Assessment requires: total bilirubin, albumin, PT/INR, Ascites assessment, and Hepatic encephalopathy assessment)
- Urine sample for urinalysis, pregnancy test (for females of child-bearing potential; in case of a positive urine test, a serum pregnancy test will be done), PPD
- Health Related Quality of Life (HRQoL) Surveys (SF-36, WPAI and CLDQ) are done only if not done within the past 24 weeks of the ED visit

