3.1.10.2. TFFU Serologically Evaluable Full Analysis Set for HBsAg Loss/Seroconversion

The TFFU Serologically Evaluable Full Analysis Set for HBsAg loss/seroconversion includes all subjects who were randomized and entered the TFFU period, and with HBsAg positive and HBsAb negative or missing at TFFU baseline. Subjects will be analyzed according to the treatment they were randomized to during the double-blind phase.

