- h Subjects who discontinue study drug due to HBsAg loss with confirmed seroconversion to anti HBs on or after the Week 24 visit, will be followed off treatment every 4 weeks for 12 weeks and then per the original study visit schedule through Week 96/ED. Subjects who have received at least one dose of study drug and permanently discontinue study drug for reasons other than HBsAg loss with confirmed seroconversion to anti HBs will be followed every 4 weeks for 24 weeks off treatment or up to initiation of appropriate, alternative HBV therapy, whichever occurs first. Initiation of appropriate, alternative HBV therapy is highly encouraged.
- i HBeAb and HBsAb reflex testing will be performed as needed.
- Resistance sequence analysis may be performed at BL for subjects with HBV DNA ≥ 69 IU/mL and may be attempted for viremic subjects (HBV DNA ≥ 69 IU/mL) at Wks 48 and 96/ED. Phenotypic analysis will be performed for subjects that are subjected to sequence analysis. As it may not be known at the time of the visit whether a subject is viremic or if it will be their last study visit, a virology sample will be collected as each visit. In the event of unconfirmed virologic rebound (HBV DNA ≥ 20 IU/mL), subjects will be asked to return to the clinic for a scheduled or unscheduled blood draw. For virologic rebound occurring within the first 12 weeks of the study, the next scheduled visit will used for follow up. For virologic rebound occurring after Week 12, the subject will return for an unscheduled visit 2 3 weeks after the date of the original test that resulted with HBV DNA virologic rebound for confirmation of virologic rebound. At this follow up visit, a serum blood sample for resistance testing will be obtained. For unscheduled visits, the subject will be required to bring their supply of study drug with them and be assessed for adherence by pill count, and if necessary, the subject will be re counseled on adherence to study medication.
- k The visit window for Week 48 visit is 14 days only.
- Serum Cystatin C will be done when eGFR_{CG} falls < 50 ml/min during blinded period of study.

- Health Related Quality of Life surveys required for Early Discontinuation (ED) visit if not done within the last 24 weeks of the expected ED visit date
- n Child Pugh Score will be assessed at Baseline (Day 1), Weeks 48 and 96. Assessment requires: total bilirubin, albumin, PT/INR, Ascites assessment, and Hepatic encephalopathy assessment

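### SAP 3.6.2 admits only on-treatment serology at Week 96, so HBsAg seroconverters who stop drug under the protocol, with a last dose before Day 586, become failures or drop out of that analysis

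*SAP*

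**What the plan says.** **Stopping and follow-up.** Protocol 3.1 says that subjects with HBsAg loss and confirmed seroconversion "should discontinue study drug within 3-6 months following confirmation of seroconversion to anti-HBs", but not before the Week 48 visit. Known bridging fibrosis or cirrhosis is handled case by case. Under Protocol 6.4.1 those who stop "will be followed off treatment every 4 weeks for 12 weeks and then per the original study visit schedule through Week 96/ED", and footnote h to the SAP's procedures table (Appendix 1) repeats this. HBV serology is drawn at the off-treatment visits (Protocol 6.4.3) and at Week 96 (6.3.2.3).

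**Analysis windows.** SAP 3.6.2 says its Tables 3-1 to 3-6 "apply only to baseline and postbaseline on-treatment assessments collected during the double-blind phase and open-label phase". For subjects in the open-label phase, on-treatment means "assessments that occurred during the period from Open-label Study Day 2 up to the Last Dose Date + 3 days". For those who never enter it, the period runs "from Study Day 2 up to and including the Last Dose Date of Blinded Study Drug + 3 days". Later results belong to treatment-free follow-up (TFFU). Table 3-5 governs HBV serology and sets Week 96 at Days 589 to 840.

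**Endpoint.** HBsAg loss and seroconversion at Weeks 48 and 96 are secondary efficacy endpoints (Protocol 8.1.3, SAP 6.2.1). SAP 6.2.2 analyses them with missing counted as failure (M=F) and with missing excluded (M=E).

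**The concern.** For these subjects, reaching the endpoint is what triggers the stop, and the stop is what removes the Week 96 result. The loss therefore falls on responders. M=F and M=E both move the Week 96 rate down, so comparing them would not reveal the problem.

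Nothing in the protocol calls for the restriction. Protocol 8.1.3 states the Week 96 serology endpoint without limiting it to on-treatment results, whereas the HBV DNA snapshot (8.6.1.1) is limited explicitly. SAP 6.3 lists only the Week 24 FibroTest as a change from the protocol's efficacy analyses. At stake is whether a named secondary endpoint counts as a non-responder a subject who seroconverted and then followed the stopping rule.

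**Working it through.** **1. The plan's own window.** The midpoint of the Week 72 and Week 96 nominal days is (504 + 672)/2 = 588, so Week 96 starts on Day 589. This reproduces Table 3-5.

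**2. Cut-off for the last dose.** A Week 96 record needs last dose + 3 ≥ 589.
- Last dose on Day 585: 585 + 3 = 588, outside the window.
- Last dose on Day 586: 586 + 3 = 589, inside.
- The earliest scheduled Week 96 visit is 672 − 7 = Day 665, which is on-treatment only if the last dose is on or after 665 − 3 = Day 662.
- For last doses on Days 586 to 661, a Week 96 value depends on an early-discontinuation (ED) or unscheduled draw within 3 days. Protocol 6.5 says "The ED Visit should be performed within 72 hours" of the last dose, but does not say explicitly that this visit applies to seroconverters who stay in the study.

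**3. When these subjects stop.** Assume that 3 to 6 months is 91 to 183 days, that confirmation falls on a nominal visit day, and that no stop precedes Day 336. Last dose = max(336, confirmation day + 91) to max(336, confirmation day + 183).

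| Confirmed at | Last dose, Study Day | Week 96 result |
|---|---|---|
| Week 24 (Day 168) | 336–351 | lost |
| Week 36 (Day 252) | 343–435 | lost |
| Week 48 (Day 336) | 427–519 | lost |
| Week 60 (Day 420) | 511–603 | lost up to Day 585 |
| Week 72 (Day 504) | 595–687 | Days 595–661 depend on an ED or unscheduled draw |

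With 84 to 168 days instead, confirmation at Week 48 gives Days 420–504 (still all lost), Week 60 gives 504–588 and Week 72 gives 588–672.

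**4. Whether another analysis restores the result.**
- The loss and seroconversion definitions in SAP 6.2.1 are tied to a visit, and no rule carries a confirmed response forward.
- The open-label evaluable set (SAP 3.1.9.2) needs HBsAg positive at open-label baseline, which excludes anyone who lost HBsAg before then. Those who lost it later are in the set but meet the same cut-off.
- The TFFU evaluable set (3.1.10.2) takes only subjects "with HBsAg positive and HBsAb negative or missing at TFFU baseline", so HBsAg-negative stoppers are out.
- Off-treatment HBsAg is summarised in the TFFU FAS, but Table 3-7 ends at follow-up Day 182. A Day 672 sample has no window if the last dose was before 672 − 182 = Day 490. For a last dose on Day 427 it is follow-up Day 672 − 427 = 245. Such results appear only in listings (SAP 6).

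**5. Size.** Protocol 1.2.3 gives Week 48 HBsAg seroconversion of 3/581 on TAF and 0/292 on TDF in the HBeAg-positive study. In the HBeAg-negative study (285 TAF, 140 TDF) no subject lost HBsAg. Protocol 8.9 assumes HBeAg-negative to HBeAg-positive of 2:1, so 230 subjects are 153.3 and 76.7.
- TAF at 2:1: 76.7 × 3/581 + 153.3 × 0/285 = 0.40. TDF: 0.
- TAF pooled without reweighting: 230 × 3/866 = 0.80 (exact 95% range 0.16 to 2.3). TDF: 230 × 0/432 = 0 (0 to 2.0).
- Each lost subject lowers the M=F rate by 1/230 = 0.43 percentage points.
- Illustration: with 3 seroconverters of whom 2 stopped early, 3/230 = 1.30% becomes 1/230 = 0.43% (M=F) or 1/228 = 0.44% (M=E). With 1 of 1 stopped, 0.43% becomes 0%.

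**The case against.** **Too few subjects to matter.** On a Poisson reading, the chance of no TAF seroconverter by Week 48 is exp(−0.40) = 67%, or exp(−0.80) = 45% pooled. Comparisons of this endpoint are exploratory (Protocol 8.6.2). This stands and limits the weight of the point. With an expected count near one, though, a single lost responder can take the reported rate to zero.

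**The response is visible elsewhere.** The subject counts at on-treatment visits, including Week 48 if converted by then, and all efficacy data are listed. True, but the Week 96 endpoint itself would still be misstated.

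**On-treatment analysis is a legitimate choice, and missing = failure is the protocol's own rule.** That would answer the point if the protocol limited Week 96 serology to on-treatment results. It does not, and it collects the data off treatment.

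**The remedy is asymmetric.** Under M=F, admitting off-treatment data only for subjects who stopped as responders can raise a rate but never lower it. The Week 48 analysis had also been done when the SAP was signed in March 2020. The exception follows the protocol's design: only this group is scheduled off drug through Week 96, while other stoppers are followed for 24 weeks or until other therapy starts. A subject whose HBsAg returns would still count as a non-responder. What stands is that a version covering the whole FAS is a useful sensitivity analysis, and that the timing of the change should be stated.

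**The day ranges are illustrative.** The protocol's wording on stopping is should, not must, and it does not say when confirmation occurs. This stands for the table, but not for the Day 586 cut-off, which follows from the SAP alone. The 0.43-point figure uses 230; the Serologically Evaluable FAS (SAP 3.1.8.2) would give a slightly different denominator.

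**Conclusion.** The concern holds. As written, SAP 3.6.2 leaves a confirmed HBsAg seroconverter whose last dose is before Day 586 without a Week 96 result, and SAP 6.2.2 then counts that subject as a failure or drops the subject. On the assumed day ranges this covers everyone confirmed at or before Week 48 who follows the stopping rule, and some confirmed at Week 60. Later stoppers, and subjects with bridging fibrosis or cirrhosis, may keep Week 96 data.

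The expected number is small, about 0.40 to 0.80 per 230 on TAF and none on TDF. Those rates come from viremic subjects at Week 48 and are only a guide to suppressed subjects at Week 96. Week 48 results, the primary endpoint, its power and the alpha-controlled tests are untouched. It should be corrected because a stated rule misclassifies responders on a named secondary endpoint, but it does not threaten the trial's main conclusions.

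**What to change.** In SAP 3.6.2 or 6.2.2, add one sentence. For Week 96 HBsAg loss and seroconversion, in subjects who stopped study drug because of confirmed HBsAg seroconversion, HBsAg and HBsAb results on Study Days 589 to 840 are assigned to Week 96 regardless of treatment status. Keep the on-treatment analysis as supportive. A version using all FAS subjects regardless of treatment is optional and would meet the asymmetry objection. Record in the SAP revision table or the CSR that the change came after the Week 48 analysis.

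Related wording to tidy at the same time:
- SAP 6.2.2 puts M=F missing subjects in the numerator as well as the denominator. For response endpoints, state that they are non-responders counted in the denominator only.
- State that HBV DNA below 20 IU/mL at Week 96 follows the snapshot definition and the exemption from missing = failure (Protocol 8.1.3, 8.3, 8.6.2).
- SAP 1.2.5 mentions only 12 weeks of follow-up after HBsAg loss. Align it with the SAP's own footnote h, which continues "then per the original study visit schedule through Week 96/ED".
- Footnote h in both documents refers to stopping on or after Week 24, while Protocol 3.1 and 6.4.1 refer to Week 48. These passages must be reconciled.

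The cost is one exception sentence, a few wording edits and a small programming change. The serology is already collected.
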